3.5.7 Prior and Concomitant Treatments

If the use of any concomitant treatment(s) becomes necessary, the treatment(s) must be recorded in the eCRF, including the name of the drug or treatment, dose, route of administration, date and time of the treatment, and indication. In the event that concomitant medication is administered, the principal investigator or qualified sub-investigator must assess the subject's eligibility of continuing the participation in the study.

The following medications/therapies are not allowed to be taken/used by subjects enrolled in this study during the trial (up to Week 52, a final follow-up visit):

- Any investigational drug
- Any therapy that may affect Alzheimer's disease, in the judgment of the investigator
- Immunosuppressant
- Cytotoxic drug
- Corticosteroids or similar steroid anti-inflammatory medication (e.g., Prednisone) on a regular basis (exceptions allowed include; regular use of steroid nasal sprays, topical steroids, and estrogen-replacement therapy)

3.5.8 Treatment Compliance

All subjects will return on Visits 4, 5, 6, 7, 8, 9, 10, 11 and 12 (Weeks 2, 4, 6, 8, 10, 12, 14, 16 and 18) for subsequent injections and Visits 13 and 14 (Weeks 30 and 52) for follow-ups.

3.6 Study Endpoints and Variables

3.6.1 Study Endpoints

Primary endpoints used to determine the safety and efficacy of AstroStem is the following:

- Number of subjects with treatment related adverse events as assessed by analysis of adverse events including symptoms, and abnormal findings on physical examination, vital signs, ECG, and standard laboratory examination results
- Change of ADAS-Cog (Alzheimer's Disease Assessment Scale-cognitive subscale) from baseline at Week 30

The **secondary endpoints** used to determine the efficacy and safety of AstroStem are the following:

- Change of MMSE (Mini-mental status examination) from baseline at Week 30
- Changes of CDR-SOB (Clinical Dementia Rating-Sum of Boxes) from baseline at Week 30
- Changes of NPI (Neuropsychiatric Inventory) from baseline at Week 30
- Changes of GDS (Geriatric Depression Scale) from baseline at Week 30
- Change of ADCS-ADL (Alzheimer's Disease Cooperative Study Activities of Daily Living) from baseline at Week 30
- Changes of C-SSRS (Columbia Suicide Severity Rating Scale) from baseline at Week 30
- Change of MRI imaging results from baseline at Week 30
- Biomarkers in blood: Amyloid beta 40, Amyloid beta 42, Amyloid precursor protein intracellular domain (AICD), soluble neuregulin-1 (sNRG-1)

3.6.2 Efficacy Variables

- ADAS-Cog at Visits 3, 6, 9, 12, 13 and 14 or Early Termination

- MMSE at Visits 1, 3, 6, 9, 12, 13 and 14 or Early Termination
- CDR-Box at Visits 3, 6, 9, 12, 13 and 14 or Early Termination
- NPI at Visits 3, 6, 9, 12, 13 and 14 or Early Termination
- GDS at Visits 3, 6, 9, 12, 13 and 14 or Early Termination
- ADCS-ADL at Visits 3, 6, 9, 12, 13 and 14 or Early Termination
- Biomarkers in blood [Amyloid beta 40, Amyloid beta 42, Amyloid precursor protein intracellular domain (AICD), soluble neuregulin-1 (sNRG-1)] at Visits 3, 13 and 14 or Early Termination

The rating scales used in this study are ADAS-Cog (Alzheimer's Disease Assessment Scale-cognitive subscale), MMSE (Mini-mental status examination), CDR-SOB (Clinical Dementia Rating-Sum of Box), NPI (Neuropsychiatric Inventory), GDS (Geriatric Depression Scale) and ADCS-ADL (Alzheimer's Disease Cooperative Study Activities). All questionnaires that are subject-administered should be completed by the subjects alone or along with caregiver at the beginning of each visit to minimize influences from other procedures to be performed at that visit. A short explanation should be given to each subject about the purpose and the necessity of these questionnaires.

3.6.3 Safety Variables

- Hematology, blood chemistry and urinalysis at Visits 1, 3, 6, 9, 12, 13 and 14 or Early Termination. See Section Appendix 1 for a complete list of laboratory tests to be done.
- ECG evaluation at Visits 1, 3, 6, 9, 12, 13 and 14 or Early Termination
- Complete physical examination at Visits 1, 3, 6, 9, 12, 13 and 14 or Early Termination
- Vital signs (sitting blood pressure, pulse, breathing, and temperature) and weight will be measured at all visits.
- MRI Scan of the brain at Visit 1, 9, 13 and 14 or Early Termination.
- C-SSRS at Visit 3, 6, 9, 12, 13, and 14 or Early Termination
- Data regarding AEs and concomitant medications will be collected at all visits

4. STUDY PROCEDURES

4.1 Screening Period

A signed and dated Institutional Review Board (IRB) approved informed consent must be obtained before any study-specific procedures are performed. Once written informed consent has been obtained, the subject will be screened to determine eligibility and document adherence to the preliminary inclusion/exclusion criteria.

4.1.1 Visit 1: Screening (Week -8)

The following screening assessments/procedures must be performed and the results documented within 2 weeks before Visit 2 unless otherwise indicated:

- Administer informed consent
- Review the inclusion and exclusion criteria (See Section 3.2)
- Record demographic data (i.e., date of birth, race and height).
- Record medical and medication history.
- Measure vital signs (sitting blood pressure, pulse, breathing, and temperature) and weight.
- Perform a complete physical examination.
- Measure 12-lead ECG.
- Collect blood and urine samples for hematology, serum chemistry, pregnancy test (only for women of childbearing potential) and urinalysis.
- Complete MMSE assessment
- Perform chest X-ray.
- Perform MRI scan including fluid-attenuation inversion recovery (FLAIR) and T2*-weighted gradient-recalled-echo (GRE) sequences.

[figure not shown]
4.1.2 Visit 2 (Week -4)

Visit 2 will occur approximately 4 weeks (\pm 1 week) after Visit 1. During this visit, the following assessments/procedures should be performed:

- Confirm eligibility and perform randomization instructed in Section 3.5.6.
- Measure vital signs (sitting blood pressure, pulse, breathing, and temperature) and weight.
- Record any changes in concomitant medications.
- Record any adverse events, if applicable.
- In sterile conditions, collect blood and harvest approximately 30 mL of fat using the syringe liposuction technique with Tumescent (or super-wet) local anesthesia (Please see the detail procedures in Appendix 9).
- Ship the packaging box containing the harvested syringes and serum tubes to the lab designated by the sponsor (pre-labeled).

4.1.3 Preparation of Final Drug Product at Lab

The following procedures for the preparation of final drug product will be performed by well-trained lab technicians at the lab designated by the sponsor. The official package containing the final drug product (syringes) will be shipped to the clinical site.

4.2 Treatment Period

4.2.1 Visit 3: Baseline (Week 0)

Visit 3 will occur approximately 4 weeks after Visit 2. During this visit, the following assessments/procedures should be performed:

- The following questionnaires will be completed: ADAS-Cog (see Appendix 2), MMSE (see Appendix 3), CDR-SOB (see Appendix 4). NPI (see Appendix 5), GDS (see Appendix 6), ADCS-ADL (see Appendix 7) and C-SSRS (see Appendix 8).
- Measure vital signs (sitting blood pressure, pulse, breathing, and temperature) and weight.
- Perform a complete physical examination.
- Measure 12-lead ECG.
- Record any changes in concomitant medications.
- Record any adverse events, if applicable.
- Collect blood and urine samples for hematology, serum chemistry, pregnancy test (only for women of childbearing potential), biomarker analysis and urinalysis.
- Collect blood for IP and ship the packaging box containing the serum tubes to the lab designated by the sponsor (Please follow the serum for IP handling instruction separately provided by the sponsor).
- Administer the AstroStem in 220 mL of saline (two times of 10 ml AstroStem in 100 mL of saline) or the same volume of saline via I.V. for 2-6 hours to patients in the treatment group and the placebo group, respectively (Please see the detail procedures in Appendix 10).

4.2.2 Visits 4, 8, 10 and 11 (Weeks 2, 10, 14 and 16)

Visits 4, 8, 10 and 11 will occur approximately 2 weeks (\pm 3 days) after the previous visit. During this visit, the following assessments/procedures should be performed:

- Measure vital signs (sitting blood pressure, pulse, breathing, and temperature) and weight.
- Record any changes in concomitant medications.
- Record any adverse events, if applicable.
- Verify if subjects are eligible to have a repeated injection by confirming subjects has not experienced infusion reaction, allergic reaction or anaphylaxis in associated with the previous study drug administration.
- Administer the AstroStem in 220 mL of saline or the same volume of saline via I.V. for 2-6 hours to patients in the treatment group and the placebo group, respectively.

4.2.3 Visits 5 and 7 (Weeks 4 and 8)

Visits 5 and 7 will occur approximately 2 weeks (\pm 3 days) after the previous visit. During this visit, the following assessments/procedures should be performed:

- Measure vital signs (sitting blood pressure, pulse, breathing, and temperature) and weight.
- Record any changes in concomitant medications.
- Record any adverse events, if applicable.
- Collect blood for IP and ship the packaging box containing the serum tubes to the lab designated by the sponsor (Please follow the serum for IP handling instruction separately provided by the sponsor).

- Verify if subjects are eligible to have a repeated injection by confirming subjects has not experienced infusion reaction, allergic reaction or anaphylaxis in associated with the previous study drug administration.
- Administer the AstroStem in 220 mL of saline or the same volume of saline via I.V. for 2-6 hours to patients in the treatment group and the placebo group, respectively.

4.2.4 Visit 6 (Week 6)

Visit 6 will occur approximately 2 weeks (\pm 3 days) after Visit 5. During this visit, the following assessments/procedures should be performed:

- Measure vital signs (sitting blood pressure, pulse, breathing, and temperature) and weight.
- Perform a complete physical examination.
- Measure 12-lead ECG.
- Record any changes in concomitant medications.
- Record any adverse events, if applicable.
- Verify if subjects are eligible to have a repeated injection by confirming subjects has not experienced infusion reaction, allergic reaction or anaphylaxis in associated with the previous study drug administration.
- The following questionnaires will be completed: ADAS-Cog (see Appendix 2), MMSE (see Appendix 3), CDR-SOB (see Appendix 4), NPI (see Appendix 5), GDS (see Appendix 6), ADCS-ADL (see Appendix 7) and C-SSRS (see Appendix 8).
- Collect blood and urine samples for hematology, serum chemistry and urinalysis.
- Administer the AstroStem in 220 mL of saline or the same volume of saline via I.V. for 2-6 hours to patients in treatment group and placebo group, respectively.

4.2.5 Visit 9 (Week 12)

Visit 9 will occur approximately 2 weeks (\pm 3 days) after Visit 8. During this visit, the following assessments/procedures should be performed:

- Measure vital signs (sitting blood pressure, pulse, breathing, and temperature) and weight.
- Perform a complete physical examination.
- Measure 12-lead ECG.
- Record any changes in concomitant medications.
- Record any adverse events, if applicable.
- Verify if subjects are eligible to have a repeated injection by confirming subjects has not experienced infusion reaction, allergic reaction or anaphylaxis in associated with the previous study drug administration.
- The following questionnaires will be completed: ADAS-Cog (see Appendix 2), MMSE (see Appendix 3), CDR-SOB (see Appendix 4), NPI (see Appendix 5), GDS (see Appendix 6), ADCS-ADL (see Appendix 7), and C-SSRS (see Appendix 8).
- Perform MRI scan including FLAIR and T2- weighted gradient-echo sequences.

- Collect blood and urine samples for hematology, serum chemistry and urinalysis.
- Collect blood for IP and ship the packaging box containing the serum tubes to the lab designated by the sponsor (Please follow the serum for IP handling instruction separately provided by the sponsor).
- Administer the AstroStem in 220 mL of saline or the same volume of saline via I.V. for 2-6 hours to patients in treatment group and placebo group, respectively.

4.2.6 Visit 12 (Week 18)

Visit 12 will occur approximately 2 weeks (\pm 3 days) after Visit 11. During this visit, the following assessments/procedures should be performed:

- The following questionnaires will be completed: ADAS-Cog (see Appendix 2), MMSE (see Appendix 3), CDR-SOB (see Appendix 4). NPI (see Appendix 5), GDS (see Appendix 6), ADCS-ADL (see Appendix 7) and C-SSRS (see Appendix 8).
- Measure vital signs (sitting blood pressure, pulse, breathing, and temperature) and weight.
- Perform a complete physical examination.
- Measure 12-lead ECG.
- Record any changes in concomitant medications.
- Record any adverse events, if applicable.
- Verify if subjects are eligible to have a repeated injection by confirming subjects has not experienced infusion reaction, allergic reaction or anaphylaxis in associated with the previous study drug administration.
- Collect blood and urine samples for hematology, serum chemistry, pregnancy test (only for women of childbearing potential) and urinalysis.
- Administer the AstroStem in 220 mL of saline or the same volume of saline via I.V. for 2-6 hours to patients in treatment group and placebo group, respectively.

4.3 Follow-up Period

4.3.1 Visit 13: 1st Follow-up Visit (Week 30)

The first follow-up visit, Visit 13, will occur approximately 12 weeks (\pm 7 days) after Visit 12. During this visit, the following assessments/procedures should be performed:

- Measure vital signs (sitting blood pressure, pulse, breathing, and temperature) and weight.
- Perform a complete physical examination.
- Measure 12-lead ECG.
- Record any changes in concomitant medications.
- Record any adverse events, if applicable.
- The following questionnaires will be completed: ADAS-Cog (see Appendix 2), MMSE (see Appendix 3), CDR-SOB (see Appendix 4). NPI (see Appendix 5), GDS (see Appendix 6), ADCS-ADL (see Appendix 7) and C-SSRS (see Appendix 8).

- Collect blood and urine samples for hematology, serum chemistry, pregnancy test (only for women of childbearing potential), biomarker analysis and urinalysis.
- Perform MRI scan including FLAIR and T2- weighted gradient-echo sequences.

4.3.2 Visit 14: Final Follow-up Visit (Week 52)

The final follow-up visit, Visit 14, will occur approximately 22 weeks (\pm 7 days) after Visit 13. During this visit, the following assessments/procedures should be performed:

- Measure vital signs (sitting blood pressure, pulse, breathing, and temperature) and weight.
- a complete physical examination.
- Measure 12-lead ECG.
- Record any changes in concomitant medications.
- Record any adverse events, if applicable.
- Perform The following questionnaires will be completed: ADAS-Cog (see Appendix 2), MMSE (see Appendix 3), CDR-SOB (see Appendix 4). NPI (see Appendix 5), GDS (see Appendix 6), ADCS-ADL (see Appendix 7), and C-SSRS (see Appendix 8).
- Collect blood and urine samples for hematology, serum chemistry, pregnancy test (only for women of childbearing potential), biomarker analysis and urinalysis.
- Perform MRI scan including FLAIR and T2- weighted gradient-echo sequences.

4.4 Early Termination Visit

If a subject will drop-out the study before Visit 14 (Week 52), the clinical site will try to schedule an early termination visit. During this visit, the following assessments and procedures should be performed:

- The following questionnaires will be completed: ADAS-Cog (see Appendix 2), MMSE (see Appendix 3), CDR-SOB (see Appendix 4). NPI (see Appendix 5), GDS (see Appendix 6), ADCS-ADL (see Appendix 7) and C-SSRS (see Appendix 8).
- Measure vital signs (sitting blood pressure, pulse, breathing, and temperature) and weight.
- Perform a complete physical examination.
- Measure 12-lead ECG.
- Record any changes in concomitant medications.
- Record any adverse events, if applicable.
- Collect blood and urine samples for hematology, serum chemistry, pregnancy test (only for women of childbearing potential), biomarker analysis and urinalysis.
- Perform MRI scan including FLAIR and T2- weighted gradient-echo sequences.

4.5 Data Quality

Monitoring and auditing procedures defined/agreed by the sponsor will be followed in compliance with current GCP guidelines. Each center will be visited at regular intervals by a monitor to ensure compliance with the study protocol, GCP guideline, and other regulatory aspects. This will include

on-site review of the eCRF for completeness and clarity, consistency with source documents, and clarification of administrative matters.

4.6 Documentation

Entries made in the eCRF must be either verifiable against source documents or have been directly entered into the eCRF, in which case the entry in the eCRF will be considered as the source data. The source data parameter to be verified and the identification of the source document must be documented. The study file and all source data should be retained/archived until notification by the sponsor for change of archive site or destruction.

5. ETHICAL AND LEGAL ASPECTS

5.1 Institutional Review Board (IRB)

Documented approval from the IRB will be obtained for all participating trial center(s)/clinic(s) prior to study start, according to GCP and applicable laws and regulations. When necessary, an extension, amendment, or renewal of the IRB approval must be obtained and also forwarded to the sponsor. The IRB must supply to the sponsor, upon request, a list of the IRB members involved in the vote and a statement to confirm that the IRB is organized and operates according to GCP and applicable laws and regulations.

5.2 Ethical Conduct of the Study

The procedures set out in this protocol, pertaining to the conduct, evaluation, and documentation of this study, are designed to ensure that the sponsor and investigator abide by GCP guidelines and under the guiding principles detailed in the Declaration of Helsinki. The study will also be carried out in keeping with applicable local laws and regulations. This may include an inspection by the sponsor representatives and/or Regulatory Authority representatives at any time. The investigator must agree to the inspection of study-related records by the Regulatory Authority/sponsor representatives, and must allow direct access to source documents to the Regulatory Authority/sponsor representatives.

Modifications to the study protocol will be implemented by the investigator only after sponsor's approval. However, the investigator may implement a deviation form, or change of the protocol to eliminate any immediate hazard(s) to the trial subjects without prior IRB/sponsor approval. The implemented deviation or change, the reasons for it and, if appropriate, the proposed amendment should be submitted to the IRB/sponsor as soon as possible. Any deviations from the protocol must be fully explained and documented by the investigator.

5.3 Regulatory Authority Approvals/Authorizations

Regulatory Authority approvals/authorizations/notifications, where required, will be in place and fully documented prior to the study's start.

5.4 Subject Information Consent

A core information and Informed Consent Form will be provided. Prior to the beginning of the study, the investigator must have the IRB written approval of the Informed Consent Form and any other written information that will be provided to the subjects. The written approval of the IRB with the approved Informed Consent Form must be in the study files.

Written informed consent must be obtained before any study specific procedure takes place. Participation in the study and date of informed consent given by the subject should be documented appropriately in the subject's files.

5.5 Insurance

All subjects participating in the study will have insurance coverage by the sponsor, which is in line with applicable laws and/or regulations.

5.6 Confidentiality

All records identifying the subject will be kept confidential and, to the extent permitted by the applicable laws and/or regulations, will not be made publicly available.

Subject names will not be supplied to the sponsor. Only the subject number and subject initials will be recorded in the eCRF, and if the subject name appears on any other document (e.g. pathologist report), it must be obliterated before a copy of the document is supplied to the sponsor. Study findings stored on a computer will be stored in accordance with local data protection laws. The subjects will be informed in writing that representatives of the sponsor, IRB, or Regulatory Authorities may inspect their medical records to verify the information collected, and that all personal information made available for inspection will be handled in strictest confidence and in accordance with local data protection laws.

Even if the results of the study are published, the subject's identity will remain confidential. The investigator will maintain a list to enable subjects' records to be identified.

6. STATISTICAL METHODS AND DETERMINATION OF SAMPLE SIZE

6.1 Statistical and Analytical Plans

6.1.1 Analytical Populations

6.1.1.1 Intent-to-Treat Population

An intent-to-treat (ITT) population will include subjects who received at least one intravenous injection and have post-injection efficacy measurements. This population will be evaluated for all efficacy variables.

6.1.1.2 Per-Protocol Population

All subjects valid for ITT who complete Visit 13 (Week 30) will be ‘valid per protocol’ (also called ‘valid for efficacy’). Additional criteria may be added prior to unblinding the study database. As with the ITT population, this per-protocol (PP) cohort will also be evaluated for all efficacy variables.

6.1.1.3 Safety Population

A safety population will include subjects who received at least one intravenous injection and have post-injection safety measurements. This population will be evaluated for all safety variables.

6.1.2 Treatment Group Comparability

Demographic variables, medical history, treatment duration, and efficacy variables at baseline will be summarized by treatment group for the subjects valid for potential safety analysis. Because, in theory, the goal of randomization is to balance out the patient characteristics, statistical tests are not planned for these variables.

6.1.3 Significance Level

The primary efficacy hypothesis test will be performed using a 5% significance level. For the secondary efficacy endpoints, hypothesis tests will be performed individually at the 5% significance level. All hypothesis tests will be performed with two-sided alternative hypotheses. No adjustments on the significance level for multiple comparisons are planned, as this is a phase 1/2 study.

6.1.4 Primary Efficacy Analyses

The primary efficacy variable is the change from Baseline on the ADAS-Cog score at Week 30. The primary efficacy variable will be summarized with means, standard deviations, medians and ranges, overall and by group. The change from Baseline ADAS-Cog score will be analyzed with Student's t-test or Kruskal-Wallis test depending on the violation of normality assumption.

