6.1.5 Secondary Efficacy Analyses

The secondary efficacy analyses are described below. They will be summarized with means, standard deviations, medians and ranges for continuous variables and with counts and percentages for categorical variables.

The percentage of subjects who show improvement will be compared between groups using chi-square test or Fisher's exact test, as appropriate. Fisher's exact test will be used if the expected frequency in any of the cells of the crosstabulation is less than 5.

Change from baseline at Week 30 in MMSE, CDR-SOB, NPI, GDS and ADCS-ADL will be compared between groups using t-test or Kruskal-Wallis tests, as appropriate. If the change is approximately normally distributed, t-test will be used. If the change is markedly non-normally distributed, Kruskal-Wallis test will be used.

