6.2 Determination of Sample Size

There was no formal sample size calculation since this is a phase 1/2 study and is not a hypothesis-driven study. The number of enrolled subjects is predefined at n=22, for 11 subjects per group.

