4.2. Adjustments for Covariates

There will be no adjustment for covariates.

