Prior and concomitant medications will be tabulated for the ITT population by WHODDE ATC level 2 classifications, preferred term, and treatment. If a subject reports the same preferred term multiple times, then the frequency of that preferred term will only be incremented by one. As with the preferred term, if a subject reports multiple medications within the same ATC level 2 classification, then the frequency of that ATC level 2 classification will only be incremented by one. Percentages will be calculated using the total number of subjects in the safety population. Each summary will be ordered by descending order of incidence of preferred term within each ATC class. Prior and concomitant medications will be included in a data listing.

4.6.5. *Treatment Compliance*

Not applicable.

4.7. *Efficacy Analyses*

The primary efficacy hypothesis test will be performed using a 5% significance level. For the secondary efficacy endpoints, hypothesis tests will be performed individually at the 5% significance level. All hypothesis tests will be performed with two-sided alternative hypotheses. No adjustments on the significance level for multiple comparisons are planned, as this is a phase 1/2 study. All efficacy analyses will be based on the ITT population.

4.7.1. *Primary Efficacy Analysis*

The primary objective of this study is to test the hypothesis that AstroStem is superior to placebo in the improvement on neurological/neurocognitive assessment from baseline to week 30 in patients with Alzheimer's Disease.

The primary analysis will evaluate the efficacy of AstroStem compared with placebo on the overall mean change from baseline to week 30 in ADAS-Cog score. The primary efficacy variable will be summarized with means, standard deviations, medians and ranges, overall and by group. The change from Baseline ADAS-Cog score will be analyzed with Student's t-test or Kruskal-Wallis test depending on the violation of normality assumption.

4.7.2. *Secondary Efficacy Analyses*

The secondary efficacy analyses will be summarized with means, standard deviations, medians and ranges for continuous variables including the changes from baseline at Week 30 in MMSE, CDR-SOB, NPI, GDS and ADCS-ADL.

These changes score from baseline at week 30 will be analyzed with Student's t-test or Kruskal-Wallis test depending on the violation of normality assumption. .

4.7.3. *Exploratory Efficacy Analyses*

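### The primary ADAS-Cog test is picked by a normality check with no stated criterion and without baseline adjustment; one pre-set ANCOVA settles the choice, though it may not add precision

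*Protocol*

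**What the plan says.** Protocol 6.1.4 gives the primary endpoint two tests: "The change from Baseline ADAS-Cog score will be analyzed with Student's t-test or Kruskal-Wallis test depending on the violation of normality assumption". The synopsis and SAP 4.7.1 carry the same rule. SAP 4.7.1 also states what is to be compared, namely AstroStem against placebo "on the overall mean change from baseline to week 30 in ADAS-Cog score".

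The nearest thing to a criterion is in Protocol 6.1.5, for the secondary scales only: "If the change is markedly non-normally distributed, Kruskal-Wallis test will be used". The t-test applies there when the change is roughly normal. No cut-off is given.

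On baseline, SAP 4.2 states: "There will be no adjustment for covariates". The score is collected at Visit 3; Protocol 3.6.2 lists "ADAS-Cog at Visits 3, 6, 9, 12, 13 and 14 or Early Termination".

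The inferential frame is in Protocol 6.1.3: "The primary efficacy hypothesis test will be performed using a 5% significance level", and "All hypothesis tests will be performed with two-sided alternative hypotheses". Protocol 6.2 sets the size: "The number of enrolled subjects is predefined at n=22, for 11 subjects per group".

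**The concern.** The t-test compares means. Kruskal-Wallis with two groups is a rank-sum test and does not estimate a difference in means. A rule that moves between them changes both the p-value and the quantity being tested, and with no criterion the move rests on someone's reading of a small sample.

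An operational rule was within reach: Protocol 6.1.5 gives an exact one for switching to Fisher's test (an expected cell count below 5). The SAP, where the gap should have been closed, repeats the protocol sentence. SAP 4.7.2 and 4.7.3 extend the open choice to five secondary scales at Week 30 and six scales at each of Visits 6, 9, 12 and 14, which is 5 + 6 × 4 = 29 further comparisons.

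Separately, randomization balances 11 per arm only loosely. A plan that excludes the baseline covariate leaves chance imbalance to whatever correction subtraction happens to give.

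**Working it through.** **Inputs.** From the documents: 11 per arm, two-sided 5%, change from Visit 3 to Week 30, no covariates. Not in the documents, so assumed: a true effect of 0.8 SD of the change score; the baseline to Week 30 correlation r; the ratio L of Week 30 SD to baseline SD; the shape of the change distribution (normal, t with 3 df, lognormal). The plan has no power figure to reproduce, because N = 22 was fixed without a calculation. For context, the exact noncentral t gives 43% power for 0.8 SD, and 80% is reached only at about 1.26 SD.

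**1. Type I error.** Simulated null trials at 11 per arm (20,000 to 40,000 per setting; Monte Carlo SE 0.1 to 0.2 points):
- Taking the smaller of the two p-values: 5.7–5.9%, with repeat runs between 5.6% and 5.9%.
- A fixed Shapiro-Wilk 5% rule (8,000 runs): 4.8–5.3%.
- With 9 per arm (an assumed 18% loss), the smaller p gives 5.9–6.3%.

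**2. How often the choice decides the result.** Share of trials in which exactly one of the two tests is significant, and power at 0.8 SD:

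| Change distribution | Disagree, null | Disagree, 0.8 SD | Power t | Power Kruskal-Wallis |
|---|---|---|---|---|
| Normal | 2% | 7% | 43% | 40% |
| t3 | 2.5% | 13% | 55% | 64% |
| Lognormal | 3% | 24% | 63% | 86% |

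**3. Effect of the missing criterion.** Shapiro-Wilk at 5% on the residuals and Shapiro-Wilk at 5% in each arm are both natural readings of the rule. At 11 per arm they select different tests in 9–16% of trials. The residual check flags t3 data in only 33% of trials, so it is also weak at this size.

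**4. Chance baseline imbalance.** The between-arm difference in baseline means has SD √(2/11) = 0.43 baseline SDs. With equal SDs (L = 1), an imbalance of that size shifts the change-score contrast by 0.43 × √((1 − r)/2) change-SDs: 0.21 at r = 0.5, 0.17 at r = 0.7, 0.10 at r = 0.9. The direction is over-correction: subtraction uses slope 1, while the regression slope is r × L = r, which is below 1.

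**5. Precision of ANCOVA against the change score.** The variance ratio is L²(1 − r²)/(1 + L² − 2rL) × (1 + 1/(N − 4)). The last factor is the price of estimating the slope: 1 + 1/18 = 1.056 at N = 22. Examples:
- L = 1, r = 0.7: 0.85 × 1.056 = 0.90.
- L = 1.2, r = 0.8: (1.44 × 0.36)/(2.44 − 1.92) × 1.056 = 0.997 × 1.056 = 1.05.

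| L | r = 0.5 | r = 0.7 | r = 0.8 | r = 0.9 |
|---|---|---|---|---|
| 1.0 | 0.79 | 0.90 | 0.95 | 1.00 |
| 1.2 | 0.92 | 1.02 | 1.05 | 1.03 |
| 1.4 | 1.00 | 1.06 | 1.03 | 0.89 |

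The worst loss in this grid is about 6%. ANCOVA power at 0.8 SD with L = 1 is 52%, 47%, 44–45% and 43% across the four correlations, against 43% for the t-test. With L = 1.2 it is 46%, 43% and 41% at r = 0.5, 0.7 and 0.8. Simulated type I error of ANCOVA at 11 per arm is 4.7–5.3%.

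**The case against.** Four points can be made for the plan.

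- **Small error cost in an exploratory trial.** Protocol 6.2 describes the study as not hypothesis-driven, and the inflation is under one point at 11 per arm. The size stands. The exemption does not: SAP 4.7.1 states a superiority hypothesis and Protocol 6.1.3 attaches a two-sided 5% test to it.
- **The check could be blinded.** A reader might infer from the wording that the test is picked after unblinding. The documents do not say so. SAP 4.1 presents the analyses as planned before final unblinding, and pooled changes can be inspected blind. What is established is only that the state of the check is unspecified.
- **Baseline is used.** A reader might infer that the plan ignores it. It does not: the endpoint is change from Visit 3. What is missing is regression adjustment. Nor can one say that a change score corrects imbalance only in part; with equal SDs it over-corrects, and under-correction needs r × L above 1.
- **ANCOVA is not the only remedy.** A fixed rank or permutation test would also remove the discretion, and under skewed or heavy-tailed changes a rank test has clearly more power (step 2). This stands as a trade-off. ANCOVA is preferred because SAP 4.7.1 targets a mean change.

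**Conclusion.** The point holds in a limited form. The primary test is left to an unstated normality criterion, the tested quantity changes with that choice, and adjustment for an available baseline score is excluded. The consequence is an undefined primary result more than an inflated one: the significance call turns on the choice in 2–3% of null trials and in 7–24% at 0.8 SD, depending on the distribution.

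A reader might also infer that ANCOVA would reliably gain precision. The documents give neither r nor the SDs, so that is not supported. With equal SDs the variance falls by 21% at r = 0.5 and not at all at r = 0.9; with L = 1.2 it can rise by about 5%. Entry limited to MMSE 16 to 26 may narrow the baseline spread and push L above 1. The case for ANCOVA rests on one pre-set test of the stated mean difference and on correcting chance imbalance. All magnitudes depend on the assumed effect, correlation, SD ratio and distributions, and on 11 evaluable subjects per arm unless stated.

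**What to change.** Replace the two-test rule with one analysis. Suggested text:

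> Week 30 change in ADAS-Cog will be analysed by ANCOVA with treatment and Visit 3 ADAS-Cog as terms, at the two-sided 5% level, reporting the adjusted mean difference, its 95% CI and the p-value. No normality pre-test will select the method. A rank-sum test, or a permutation test of the adjusted difference, is the sensitivity analysis and will be reported whatever the distribution.

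Keep one of the two sensitivity tests when finalising the text. Apply the same rule in the synopsis, Protocol 6.1.4 and 6.1.5, and SAP 4.7.1 to 4.7.3, using each scale's own baseline, so that the old rule survives nowhere. Rewrite SAP 4.2, rather than delete it, to name the baseline score of the analysed scale as the only covariate. Do this before unblinding and date the revision.

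Cost: no new data, and one degree of freedom (error df 20 to 19). The variance may be up to about 6% higher in unfavourable cases, and power lower than a rank test if changes are strongly skewed or heavy-tailed. A protocol amendment may be needed, since SAP 4.1 requires one when a principal feature changes. The change does not deal with missing Week 30 scores, which need their own provision.
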